7.9.1 Primary Safety Objective

Primary Safety Objective

To demonstrate that the primary safety event rate associated with the DiamondTemp ablation system is lower than the pre-specified Objective Performance Criterion (OPC).

Hypothesis

 $H_0: P \geqslant P_0$

 $H_1: P < P_0$

where $P_0 = 11.5\%$ (Safety OPC), and lower event rates are better.

Endpoint Definition and Derivation

Revision 1 Page 9 of 18

The primary safety endpoint is defined as freedom from a composite of serious adverse events (SAEs) occurring within 7 days, procedure and/or device-related significant pericardial effusion that occurs within 30 days, and severe or clinically symptomatic pulmonary vein stenosis and atrioesophageal fistula through 6 months post-index ablation procedure, as adjudicated by an independent Clinical Events Committee (CEC) for relatedness to the procedure or device.

The primary safety device- or procedure-related SAE composite will be the combined rate of the following events:

- Atrioesophageal fistula
- Bleeding complication
- Cardiac tamponade / perforation
- Death
- Extended hospitalization
- Myocardial infarction
- Pericarditis
- Phrenic nerve paralysis
- Pulmonary edema
- Pulmonary vein stenosis
- Significant pericardial effusion
- Stroke / CVA
- Thromboembolism
- Transient ischemic attack (TIA)
- Vagal nerve injury
- Vascular access complications

Performance Requirements

The null hypothesis will be rejected if the one-sided 97.5% upper confidence bound of the primary safety event rate is lower than 11.5%.

Rationale for Performance Criteria

This performance goal was derived from a point estimate of 7% and a margin of indifference of 4.5%. This point estimate value was determined from a review of the FDA publicly available information combined with the published literature for all FDA approved medical device trials for Atrial Fibrillation treatment¹ and some other studies² on ablation treatment for Atrial Fibrillation. Based on the Sponsor's

Wilbur, et al. JAMA Vol. 303, No. 4. P333-340.

https://www.accessdata.fda.gov/cdrh docs/pdf3/P030031S011b.pdf https://www.accessdata.fda.gov/cdrh_docs/pdf15/P150026B.pdf Dukkipati, et al. JACC Vol 66. No.12, 2015. p1350-1360.

https://www.accessdata.fda.gov/cdrh_docs/pdf10/P100010b.pdf

[figure not shown]
Natale, et al. JACC Vol.64, No.7, 2014. P 647-656.

The main analysis of the primary safety objective will be based on the mITT population, which includes all subjects who sign informed consent, meet eligibility criteria and attempt study treatment (i.e., catheter inserted into vasculature). Additionally, sensitivity analysis for the primary safety objective will be conducted on the Per-Protocol population, which includes all mITT subjects who do not have any major protocol violations (i.e., eligibility criteria violations, or ablation treatment with a non-study catheter), and the ITT population, which includes all subjects who sign informed consent and attempt study treatment.

7.9.2 Primary Effectiveness Objective

Primary Effectiveness Objective

To demonstrate that the primary effectiveness rate associated with the DiamondTemp ablation system is higher than the pre-specified Objective Performance Criterion (OPC).

Hypothesis

Revision 1

Page 11 of 18

 H_0 : $P \leq P_0$

 $H_1: P > P_0$

where $P_0 = 40\%$ (Effectiveness OPC), and higher effectiveness rates are better.

Endpoint Definition and Derivation

The primary effectiveness endpoint is defined as freedom from documented Atrial Fibrillation (AF), Atrial Flutter* (AFL) and Atrial Tachycardia (AT) episodes following the blanking period (3-month followup post-ablation procedure) through the end of the effectiveness evaluation period (12-month followup post-ablation procedure).

An effectiveness failure is defined by any of the following events:

- Inability to electrically isolate all accessible targeted pulmonary veins during the ablation procedure.
- Documented episodes of AF, AFL or AT lasting ≥ 30 seconds in duration as evidenced by electrocardiographic data during the effectiveness evaluation period.
- DC cardioversion for AF, AFL or AT during the effectiveness evaluation period.
- A repeat ablation procedure to treat AF, AFL or AT during the effectiveness evaluation period.
- Use of a new or previously failed anti-arrhythmic drug (AAD) at a dose greater than the highest ineffective dose for AF during the effectiveness evaluation period.
- Use of a non-study device for ablation of any AF targets during the index or repeat ablation procedure during the blanking period.
- More than one (1) repeat ablation procedure during the blanking period.

The blanking period for a subject starts on the date of the index ablation procedure (day 0) and ends on day 90 post index ablation.

The effectiveness evaluation period for a subject starts on day 91 post index ablation and ends on the study exit date or day 410 post index ablation (i.e., close of the 12-month visit window), whichever is earlier.

If a primary effectiveness failure event occurs post day 365 and within the effectiveness evaluation period, the date of the event will be set to day 365 so that these events will be accounted for in the 12month Kaplan-Meier estimate of the primary effectiveness endpoint.

Performance Requirements

The null hypothesis will be rejected if the one-sided 97.5% lower confidence bound of the primary effectiveness rate is greater than 40%.

[figure not shown]
Rationale for Performance Criteria

The performance goal was derived based on the minimum 12-month success rate for persistent AF recommended in the 2017 HRS Expert Consensus Statement on Catheter and Surgical Ablation of AF.

^{*} Occurrence and/or ablation of cavotricuspid isthmus (CTI)-dependent AFL, as confirmed by entrainment maneuvers during EP testing at any time during this study is not a primary effectiveness failure because it is not considered an iatrogenic arrhythmia following a left atrial ablation procedure for AF.

Revision 1

Page 12 of 18

Analysis Methods

The components of the primary effectiveness composite endpoint will be summarized to show the number and percentage of subjects meeting each component.

The primary effectiveness rate will be analyzed using the Kaplan-Meier method with the log-log transformation to compute the two-sided 95% confidence interval. The null hypothesis will be rejected if the one-sided 97.5% lower confidence bound of the primary effectiveness rate is greater than 40%.

Additionally, a corresponding one-sided p-value may be constructed as follows. First compute the zstatistic using the below formula:

$$z = \frac{\log(-\log(S(t))) - \log(-\log(0.4))}{\sqrt{\sigma(t)^2/(S(t) * \log(S(t)))^2}}$$

Where S(t) is the Kaplan-Meier estimate of the primary effectiveness rate at 12 months (365 days) post index ablation, and $\sigma^2(t)$ is the Greenwood's estimate of the variance of the survivor function S(t) at time t. The one-sided p-value will then be computed from the standard normal distribution as P(Z<z), which is the area of the standard normal distribution less than z since log(-log(S(t))) will be less than log(-log(0.4)) if S(t) > 0.4.

The following subgroup analyses are prospectively defined: geography (US/Canada and Europe), gender (female and male), and age (≤65 and >65 years). The log-rank test will be used to test homogeneity of the primary effectiveness endpoint results between the subgroups.

Determination of Subjects/Data for Analysis

The main analysis of the primary effectiveness objective will be based on the mITT population, which includes all subjects who sign informed consent, meet eligibility criteria and attempt study treatment (i.e., catheter inserted into vasculature). Additionally, sensitivity analysis for the primary effectiveness objective will be conducted on the Per-Protocol population, which includes all mITT subjects who do not have any major protocol violations (i.e., eligibility criteria violations, or ablation treatment with a nonstudy catheter), and the ITT population, which includes all subjects who sign informed consent and attempt study treatment.

[figure not shown]

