Extended hospitalization	Extended hospital stay or re-hospitalization that is related to the procedure or device that is not: 
 • a planned hospitalization for a pre-existing condition, or procedure required by the Clinical Investigational Plan (including repeat ablation procedure), without serious deterioration in health. • hospitalizations due to recurrent AF/AT/AFL or prolonged hospitalization during the 30 days following procedure to adjust anticoagulation or anti-arrhythmia regimen or to administer diuretic medication.
Effectiveness Evaluation Period	The period between subject's 3-month follow-up visit and 12-month follow-up visit during which the primary effectiveness endpoint will be assessed.
Enrolled Subject	All subjects who sign ICF.
Heart block	Damage to the heart's electrical system that controls heart rhythm.
Hemoptysis	Coughing up blood.
Femoral (groin) hematoma	Bleeding at the catheter insertion site that causes swelling or a pocket of blood. May need to be drained or require additional procedure.
Long Standing Persistent AF	Long-standing persistent AF is defined as continuous AF of greater than 12 months duration.
Myocardial infarction	MI as it relates to AF ablation resulting in the presence of any one of the following criteria: 
 • ECG changes indicative of new ischemia that persist for > 1 hour development of new pathological Q waves on an ECG • imaging evidence of new loss of viable myocardium or new regional wall motion abnormality
Paroxysmal Atrial Fibrillation (PAF)	Recurrent Atrial Fibrillation that last \geq 30 seconds and terminates spontaneously within 7 days.
Pericardial effusion	Accumulation of blood between heart and lining of the heart (pericardium). It is not uncommon to observe "trace" pericardial effusion following AF ablation. Trace effusion that does not need intervention is not considered a serious AE.
Persistent Atrial Fibrillation (PeAF)	Recurrent Atrial Fibrillation that lasts \geq 7 days and does not terminate spontaneously.
Self-Limiting Pericarditis	Pleuritic chest discomfort with or without pericardial rub and ECG changes and did not require additional hospitalization. Generally, not an SAE.
Serious Pericarditis	Pericarditis resulting in an effusion that leads to hemodynamic compromise, requires pericardiocentesis, prolongs hospitalization > 48 hours or persists for more than 30 days following procedure.

DIAMOND-AF II Clinical Investigation Plan

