10.7.6 Twelve Month Follow-Up Visit

All subjects must be evaluated twelve-months (365 ± 45 days) following the index ablation procedure.

During this follow-up visit, the following will be performed:

- Perform a limited physical exam (weight, resting heart rate, and blood pressure).
- Assess the subject for any new adverse events and inquire about resolution of any previously reported events(s).
 - Subjects who have experienced symptoms or adverse events suggestive of PV stenosis are required to receive a chest CT or MRI scan to rule out PV stenosis.
 - Perform a 12-lead ECG.
 - Report the absence or presence of Atrial Fibrillation or other atrial tachyarrhythmia.
- Record any medication changes.
- Review event monitor data for recordings made due to symptomatic episodes of arrhythmias (if applicable) since the last follow-up and the event monitor data from the two (2) required monthly recordings.
- Subjects will be instructed on how to use the event monitor to capture 24-hour Holter reading and the data will be transmitted remotely to the Corelab.
- Administer a follow-up QOL assessment (AFEQT Questionnaire).
- Administer a follow-up NIH Stroke Scale assessment.

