10.10 Study Completion

It is the intent of the protocol that all subjects will be followed for a minimum of 12 months post procedure. Documentation of study completion will be required for all subjects, independent of the point at which they complete the study (including screening failure, early withdrawal or loss to follow-up as applicable). Subjects will be followed by standard of care after Clinical Investigation has been completed.

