13.3 CRO/Core Lab(s)

A designated contract research organization (CRO) will provide centers and/or subjects with instructions and training on the use of an event monitors that serves as a hand-held event recorder for short duration recordings and 24 hour Holter monitors.

Subjects will be provided with an event monitor prior to discharge from the hospital and instructed to collect 1-minute ECG recordings with their event monitor if they experience AF symptoms throughout the study. Additionally, subjects will be required to collect 1-minute ECG recordings with their event monitor two times per month starting at the end of the blanking period to the 12-month follow up visit. Recordings made due to symptomatic episodes during the effectiveness evaluation period may count towards the scheduled, required monthly recordings.

The event monitors will be configured to automatically transmit recordings securely and wirelessly to the Core Lab. All events will be analyzed by the Core Lab to determine arrhythmia recurrence. The company will identify the subject's transmitted rhythm and send reports to the investigational center within 72 hours. If there is discordance between the Core Lab's rhythm analysis in the report and the Investigator, a third-party cardiologist will be used for final rhythm determination. All event monitors should be returned to the Core Lab after a subject completes the study.

Subjects will be provided instructions on how to collect a 24 hour Holter reading with the event monitor provided for event monitoring during the 3, 6 and 12 months post-ablation procedure follow-up visit windows.

The Core Lab will review, analyze and report on all event and Holter recordings as well as the 12-lead ECGs taken at the 3, 6 and 12-month follow-up visits.

14. Statistical Design and Methods

Before database lock, a Statistical Analysis Plan (SAP) will be prepared to provide full details of all planned analyses. The analyses presented here represent an outline of the intended methodology. Any change to the data analysis methods described in the Clinical Investigation Plan will require an amendment only if it changes a principal feature of the CIP. Any other change to the data analysis methods described in the CIP, and the justification for making the change, will be described in the clinical study report.

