7.4 Handling of Missing, Unused, and Spurious Data and Dropouts

All available data will be used in data listings and tabulations.

Missing data due to early dropout on the primary endpoints may occur if a subject receives study treatment but discontinues prematurely from the study without experiencing a primary safety or effectiveness failure event.

The main analysis of the primary objectives will use available data with no imputations for missing data, where subjects who discontinue prematurely will be censored at their last study contact date in the Kaplan-Meier analysis.

Additionally, to assess the potential impact of missing data due to early dropout on the primary objectives, a tipping point analysis will be performed where subjects who discontinue prematurely will be iteratively imputed as failures in the order of their censoring times. The tipping point is defined as the number of imputed failures when the one-sided 97.5% confidence bound of the endpoint estimate crosses the performance goal (11.5% for primary safety and 40% for primary effectiveness).

Analysis of the secondary and ancillary objectives and any other study data will use available data with no imputations for missing data.

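### SAP 7.9.2 moves failures on days 366–410 back to day 365 but has no rule for event-free completers who exit on days 320–364, so by default Kaplan–Meier understates freedom through the 12-month visit unless exits are late

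*SAP*

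**What the plan says.** - **Visit window.** Protocol 10.7.6: "All subjects must be evaluated twelve-months (365 ± 45 days) following the index ablation procedure". That is days 320 to 410.
- **Evaluation period.** SAP 7.9.2: it "starts on day 91 post index ablation and ends on the study exit date or day 410 post index ablation", whichever comes first. Protocol 2.2 defines the same period as the time between the "3-month follow-up visit and 12-month follow-up visit during which the primary effectiveness endpoint will be assessed".
- **Late failures.** SAP 7.9.2: if a failure falls after day 365 but within the evaluation period, "the date of the event will be set to day 365 so that these events will be accounted for".
- **Time point.** SAP 7.9.2, Analysis Methods, evaluates the Kaplan–Meier estimate at day 365 with a log-log interval. Success requires the one-sided 97.5% lower bound to exceed 40%.
- **Censoring.** SAP 7.4 uses available data without imputation, "where subjects who discontinue prematurely will be censored at their last study contact date in the Kaplan-Meier analysis". The tipping-point analysis covers the same group. This is the only censoring rule given.
- **Monitoring.** Protocol 13.3 schedules event-monitor recordings "two times per month starting at the end of the blanking period to the 12-month follow up visit", plus a 24-hour Holter in the 3-, 6- and 12-month windows.
- **Intended follow-up.** Protocol 10.10 states the intent that "all subjects will be followed for a minimum of 12 months post procedure". Nothing bars exit at an in-window visit before day 365.

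**The concern.** The SAP recognises that a ±45-day window does not fit a fixed day-365 estimate, but it resolves this for failures only. A subject seen on day 390 with a failure is counted at day 365. A subject seen on day 340 without one has no written treatment. This subject has completed the study, so the rule for premature discontinuation does not apply. With the evaluation period ending at exit and no imputation, a programmer would naturally censor at day 340.

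Late failures are then pulled back onto a day-365 risk set from which the early successes have gone. The result does not estimate freedom through the 12-month visit. It does not estimate strict day-365 freedom either, because failures after day 365 are counted.

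Trial success depends on this analysis. A downward bias lowers power below the stated 86%. Left unwritten, the choice would be made in programming, after exit dates are known, in an open single-arm trial.

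**Working it through.** **1. The plan's own figure.** SAP section 6 gives n = 274, 49% against 40%, one-sided alpha 0.025, power 86%. By the normal approximation with null variance:

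- critical value = 0.40 + 1.96 × √(0.40 × 0.60 / 274) = 0.40 + 1.96 × 0.0296 = 0.4580
- power = Φ[(0.49 − 0.4580) / √(0.49 × 0.51 / 274)] = Φ(0.0320 / 0.0302) = 85.5%

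The stated figure is reproduced. Allowing for 12% dropout, 274 / 0.88 = 312 subjects.

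**2. The mechanism by hand (invented numbers).** Of 320 subjects, 160 are event-free at day 319. Eighty are seen on day 340 (8 fail) and 80 on day 390 (8 fail).

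- Actual freedom through the visit: 144/320 = 45.0%.
- Default Kaplan–Meier: on day 340, 8 of 160 fail and 72 event-free completers are censored. The 8 failures from day 390 are re-dated to day 365, where 80 remain at risk. S = 0.5 × 152/160 × 72/80 = 42.75%.
- Completers carried to day 365: the 72 stay in the risk set. S = 0.5 × 152/160 × 144/152 = 45.0%.

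**3. Size by simulation.** From the SAP: 312 subjects, 12% dropout, 40% goal, Kaplan–Meier at day 365, Greenwood variance, log-log bound. Assumed, not in the documents: exit on the visit day, the exit-day distribution, 10% failure at day 91 followed by a constant hazard, and 5% or 0% of event-free subjects found in AF at the visit. The hazard is set so that true freedom through the visit is 49%. There were 2,000 trials per scenario, with Monte Carlo error of about 1 point on power. The low end of each default range is 5% detection and the high end is 0%.

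| Exit day | Power, default | Power, completers carried to 365 |
|---|---|---|
| N(385, SD 10) | 84% | 84–85% |
| N(375, SD 10) | 79–83% | 86% |
| N(365, SD 10) | 55–75% | 85% |
| N(365, SD 15) | 47–69% | 85% |
| Uniform 320–410 | 33–56% | 85–87% |
| N(350, SD 15) | 13–47% | 84–86% |

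The mean default estimate is 49% for N(385, 10), 46–48% for N(365, 15) and 43–47% for N(350, 15). The mean day-365 risk set, default against carried forward, is 138–144 against 141–147 for N(385, 10), 68–74 against 136–141 for exits centred on day 365, and 22–23 against about 135 for N(350, 15).

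**4. A second model.** Here the only first failures on days 320–410 are those found at the visit (3,000 runs per cell). For detection of 3%, 5% and 10%:

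- Exits N(365, 15): default estimate 48.1%, 47.3%, 46.0%; power 74%, 64%, 44%.
- Exits N(375, 15): default estimate 48.6%, 48.3%, 47.6%; power 82%, 78%, 69%.
- Completers carried to day 365: estimate 48.9–49.1%, power about 85–86%.
- All exits on or after day 365: the two methods are identical.

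**5. False-positive rate.** At a true 40% through the visit, the first model rejects in 0.05–2.2% of trials by default and 2.1–3.0% with completers carried forward.

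**6. Timing related to outcome.** With N(365, 15) and 5% detection, visit-detected subjects attended 30 days early, 15 days early, on time or 15 days late. Default power was 67%, 60%, 49% and 43%, against 85–86% with completers carried forward.

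**The case against.** **The bias depends on the estimand.** The SAP evaluates S(t) at 365 days and ties the 40% goal to a 12-month rate. Protocol Table 8 and its footnote E describe the evaluation period in months, not by visit. Against strict day-365 freedom with a constant hazard and all exits on days 320–364, default Kaplan–Meier is unbiased (49.1% against 49.0%), while carrying completers forward gives 52.0%. With all exits on days 365–410, the written re-dating rule alone lowers the estimate to 46.3%. This stands as a reason to name the estimand. It does not remove the problem: SAP 7.9.2 defines the endpoint through the end of the evaluation period, which Protocol 2.2 ends at the 12-month visit, and re-dating failures from after day 365 makes no sense for a strict day-365 quantity.

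**The remedy has a cost.** It credits up to 45 unobserved days as event-free. At a true day-365 rate of 40% (no visit detection), it rejects in 8.7% of trials for N(350, 15), and in 1.9–2.7% for exits centred on day 365. This stands, and it is why a sensitivity analysis at actual exit is needed.

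**The size is assumed.** It is. If sites honour the intended minimum of 12 months, most exits fall after day 365 and the effect is small or nil.

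**Censoring at last follow-up is ordinary practice.** SAP section 8 requires independent programming of the primary analyses, and SAP 7.11 requires changes to be justified in the report. These limit silent choices but do not supply the missing rule.

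**Conclusion.** The concern holds. The SAP treats the two halves of the visit window differently, and following its text with ordinary Kaplan–Meier gives too low an estimate of freedom through the 12-month visit whenever event-free completers leave before day 365 and some failures are dated after them. The direction assumes that visit timing is unrelated to outcome, and it persisted in the timing variants tried.

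The size cannot be fixed from the documents. In the scenarios tried, the loss of power runs from nothing or about 1 point (exits around day 385) through 3–7 points (around day 375) to 16–38 points (around day 365, SD 15); earlier exits cost more. The error is conservative and does not produce a false claim of effectiveness. It should be fixed before database lock. Confidence is medium because the exit-day distribution is unknown.

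**What to change.** In SAP 7.9.2:

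1. State that the estimand is freedom from failure through the 12-month visit (days 320–410).
2. Keep the re-dating of late failures to day 365.
3. Add that subjects who complete the 12-month visit in window, with rhythm data and without a failure, count as event-free through day 365, and are censored on that day after any events.
4. Add a sensitivity analysis that censors these subjects at their actual exit date, and report the distribution of exit days.

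SAP 7.4 should also say that such completers are not dropouts for the tipping-point analysis. The stated minimum of 12 months' follow-up and the 365 ± 45 day window should be reconciled.

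The cost is a few SAP sentences, one programming line and one extra table, with no new data. The report should disclose that up to 45 unobserved days are credited as event-free, and that on a strict day-365 reading this can inflate the false-positive rate if exits are mostly early.
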